#### Sensitivity Analyses – Per Protocol to Investigate the Impact of Protocol 9.3.2.2.2. Violators

To investigate the impact of non-compliance and protocol violators a Per Protocol analysis will also be performed for the primary endpoint of decline in FVC using the random coefficient regression model. Protocol violations potentially impacting the results will be excluded and *identified before database lock and unblinding for the final analysis.* 

This approach provides another estimand than the primary one, namely the estimate in the population of subjects who take treatment according to protocol.

# 9.3.2.2.3. Sensitivity On-treatment Analysis

The same random coefficient regression model will be run for the rate of decline in FVC, using only the data up to the last intake of IP. Data after lung transplant and taken post-bronchodilator will be excluded.

This approach provides another estimand than the primary one, namely the estimate in the population of subjects who are on treatment.

# 9.3.2.2.4. Sensitivity Analysis Including Data After Lung Transplant

The same random coefficient regression model will be run including all data, also after lung transplant.

# 9.3.2.2.5. Sensitivity Analysis on All Study Data (also beyond Week 52)

The same random coefficient regression model will be run using all data up to the end of the study for FVC in mL and percent predicted FVC. Data after lung transplant and taken postbronchodilator will be excluded.

This approach provides another estimate of the primary estimand.

#### 9.3.2.2.6. Sensitivity Analysis for Completers versus those Who Discontinued Early

The same random coefficient regression model will be run up to Week 52, for those who completed the study up to Week 52 separately from those who discontinued the study before Week 52.

#### 9.3.2.2.7. Sensitivity Analyses to Investigate the Impact of Missing Data – Control-Based Pattern Mixture Approach

Data after lung transplant and taken post-bronchodilator will be excluded.

Non-monotone missing data and missing data at visits before Week 52 will not be imputed. This assumes that the number of non-monotone missing data is either negligible or MAR, which is probably a reasonable assumption.

Multiple imputations will be used to handle missing data at Week 52. The imputation model is similar to the random coefficient regression model of the primary analysis.

In the pattern mixture approach, patterns of missing data are defined by subjects being classified in the following five categories:

- 1. Those with Week 52 data who received treatment till Week 52
- 2. Those with Week 52 data who discontinued treatment before Week 52
- 3. Those without Week 52 data who discontinued treatment before Week 52 and are still alive
- 4. Those without Week 52 data and continued treatment till Week 52 or later
- 5. Those who died before Week 52.

The number of imputations will be set to 1000 in order to ensure adequate efficiency for the estimation of the missing data. For each imputed dataset, the same model will be run as for the primary analysis and results will be combined using the standard multiple imputations approach of (Rubin, 1987). Imputations of the missing Week 52 value will be based on the estimates of the slope (SE), using data from prespecified groups depending on the assumptions. The assumptions behind are that the rate of decline in FVC in the subset of subjects imputed is similar to the rate of decline in the subset used for the imputation. A frequency table will be provided of the number (%) of subjects in each pattern.

Given the groups may become small, the strata with SOC (either nintedanib or pirfenidone) will be combined and the combined stratum with 2 levels (nintedanib or pirfenidone vs neither) will be used. If the groups are still very small and less than 10% of subjects discontinue this approach will not be performed and will only be performed on the pooled data.

*Appendix 2 provides more information on the multiple imputations approach.* 

#### Pattern Mixture Approach 1:

Pattern 3 will be imputed based on the data from Pattern 2 for the same treatment group and combined stratum (with 2 levels nintedanib or pirfenidone vs neither).

Pattern 4 will be imputed based on data from Pattern 1 for the same treatment group and combined stratum

Pattern 5 will be imputed based on data from the placebo groups of Pattern 2 for the same combined stratum.

This approach assumes that subjects who discontinue and are alive have the same rate of decline as the other subjects in the same treatment group and combined stratum, while subjects who died have a rate of decline similar to the discontinued placebo subjects in the same stratum after their last available FVC value.

#### Pattern Mixture Approach 2:

Patterns 3, 4, and 5 will be imputed based on the data from Pattern 1, 2 placebo subjects in the same combined stratum. This is a conservative approach which assumes that subjects who discontinued IP have a similar rate of decline in FVC as the placebo subjects after discontinuation.

#### Note:

The missing data will be investigated during the study in a blinded manner, especially if the monotone missingness assumption is reasonable, especially in the context of the bronchodilators use. If a high percentage of data is missing in a non-monotone pattern, appropriate measures will be taken (e.g. using an Markov chain Monte Carlo imputation of this data).

# 9.3.2.2.8. Sensitivity Analyses to Investigate the Impact of Changes in Standard of Care (Stratum)

Data after lung transplant and taken post-bronchodilator will be excluded. The below sensitivity analyses will be performed for the primary endpoint of annual rate of decline in FVC using the random coefficient regression model.

#### Sensitivity Analysis 1:

Subjects who were on the same standard of care less than 75% of the time will be excluded, i.e. in the 'neither' stratum, subjects will be excluded if they took either nintedanib or pirfenidone for more than 25% of the time, and in the 'nintedanib' and 'pirfenidone' strata they will be excluded if they did not take the SOC from their stratum for at least 75% of the time up to Week 52. Results will be presented overall and by stratum.

#### Sensitivity Analysis 2:

A similar approach as sensitivity analysis 1 will be performed combining the 'nintedanib' and 'pirfenidone' strata. In other words, if a patient starts on nintedanib treatment and

switches to pirfenidone or vice versa, they will be considered as still being on SOC for the calculation of the 75% of time on SOC.

The pattern of changes in SOC will be evaluated during the course of the study in a blinded (to randomization) manner and additional sensitivity analyses may be added as deemed necessary.

# 9.3.2.3. First Key Secondary Endpoint – Disease Progression

Disease progression is defined as the composite endpoint of first occurrence of  $\geq 10\%$  absolute decline in percent predicted forced vital capacity (%FVC) or all-cause mortality at 52 weeks. The number (%) of subjects who experience disease progression up to Week 52 will be presented and analyzed using logistic regression with similar factors in the model as for FVC rate of decline. The odds ratios (with 95% CI) versus placebo will be estimated from the model. This analysis corresponds to the key secondary endpoint and will be used in the multiplicity approach.

A similar summary analysis will also be provided by stratification factor (standard of care).

# 9.3.2.4. Other Spirometry Endpoints

The same will be used to describe the disease progression up to the end of the study.

Additionally, the two components of this composite endpoint of disease progression will also be summarized separately (number of subjects who died and number of subjects have either an absolute decline of 10 percentage point or more in percent predicted FVC).

Furthermore, to account for the differential periods of observation in the study a time to event analysis similar as described below for time to respiratory hospitalization, will be used to analyze the composite endpoint of percent predicted FVC decline and mortality up to the end of the study. See below for details on analyses of time to event endpoints.

In addition, a cumulative incidence table and graph will be presented for absolute change from baseline in percent predicted FVC per time point and worst-case up to the end of the study for the categories  $\leq$ -10,  $\leq$ -9,  $\leq$ -8,...,  $\leq$ 0, ...,  $\leq$ 8,  $\leq$ 9,  $\leq$ 10, by treatment group.

# 9.3.3. Second Key Secondary Endpoint - Time to First Respiratory-related Hospitalization until the end of the study

Respiratory hospitalizations will be adjudicated by the CEAC. The analysis will be based on the results from the adjudication, not on the investigator-reported information. Differences will be investigated and listed, if any.

The number (%) of subjects with an event during the study will be summarized as well as the number of events per 100 patients-years of follow-up. In addition, time to first event will be graphically displayed and tabulated (at each planned time point as described in Section 6.3, Week 2, Week 4, etc, and last available time point) using Kaplan-Meier estimates.

A Cox proportional hazards model with terms for age, sex, height, and stratum will be used to estimate the hazard ratios (and 95% CI) for each dose compared to placebo and to compare the active doses to placebo.

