2. INTRODUCTION

For details of GLPG1690, refer to the Investigator's Brochure (IB) (Edition 6, 28-June-2019) and any relevant updates/addenda/errata.

This clinical study will be conducted in accordance with the current International Council for Harmonisation of Technical Requirements for Pharmaceuticals for Human Use - Good Clinical Practice (ICH-GCP) Guideline E6 (see also Section 10).

Idiopathic Pulmonary Fibrosis

Idiopathic pulmonary fibrosis (IPF) is a chronic, progressive, severely debilitating, and ultimately lethal lung disease predominantly affecting elderly male smokers or ex-smokers with a median age of 65 to 70 years [5]. The disease is characterized by progressive worsening of dyspnea and lung function and is associated with a poor prognosis (i.e. median survival of 2-5 years following diagnosis) [4, 12, 14, 18, 28].

The estimated IPF prevalence ranges from 14.0 to 27.9 cases per 100,000 population in the United States and from 1.3 to 23.4 cases per 100,000 population in Europe (data from 1990-2011). The estimated IPF incidence in these studies ranges from 6.8 to 8.8 cases per 100,000 population in the United States and from 0.2 to 7.4 cases per 100,000 population in Europe [8, 22, 31, 38].

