 - 9.1 In a stable condition and suitable for study participation based on the results of a medical history, physical examination, vital signs, 12-lead ECG, and laboratory evaluation. Stable condition is based on the clinical judgment of the investigator; co-morbidities should be treated according to the local applicable guidelines. Concomitant medication for chronic co-morbidities should have been stable from 4 weeks prior to screening and during the screening period (stable defined as no clinically relevant change according to the investigator's judgment).
10. Estimated minimum life expectancy of at least 30 months for non-IPF related disease in the opinion of the investigator.
11. Male subjects and female subjects of childbearing potential agree to use highly effective contraception/preventive exposure measures (as described in Section 4.5.3.1) from the time of first dose of IMP (for the male subject) or the signing of the ICF (for the female

subject), during the study, and until 90 days (male) or 30 days (female) after the last dose of IMP.

12. Criterion modified per amendment.

12.1 Able to walk at least 150 meters during the 6MWT at screening Visit 1; without having a contraindication to perform the 6MWT (see [Appendix 10](#)) or without a condition putting the subject at risk of falling during the test (investigator's discretion). The use of a cane is allowed, the use of a stroller is not allowed at all for any condition. At Visit 2, for the oxygen titration test, resting SpO₂ should be $\geq 88\%$ with maximum 6 L O₂/minute; during the walk, SpO₂ should be $\geq 83\%$ with 6 L O₂/minute or $\geq 88\%$ with 0, 2 or 4 L O₂/minute.

13. Able to read and complete the EQ-5D, SGRQ, LCQ, K-BILD questionnaire, and VAS by themselves.

14. Able to understand the importance of adherence, and willing to comply to study treatment, study procedures and requirements as per study protocol, including the concomitant medication restrictions (described in [Section 4.5.3.2](#)).

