#### For endpoints not including vital status:

The last contact, not including mortality information is defined as the latest date collected in the eCRF from the date of death, visit dates, AE dates, concomitant treatment dates, drug intake dates or laboratory test dates, study completion date. Information from the vital status form is not to be taken into account for this calculation.

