#### Censoring

Time to event endpoints are defined from the date of first dose of IP.

If the subject did not have an event, the time to event will be censored at the last contact date, as defined in Section 6.5.

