#### 9.3.3.1. Other Adjudicated Events (Secondary) Endpoints

A time to (first) event analysis will be conducted for each of the following secondary endpoints:

- Mortality: all-cause and respiratory-related
- Hospitalization: all-cause
- Hospitalization for non-elective Lung transplant
- Acute IPF exacerbation
- All-cause mortality or hospitalization for non-elective lung transplant
- All-cause mortality, or hospitalization for non-elective lung transplant, or hospitalization for qualifying for lung transplant
- All-cause mortality, hospitalization for ≥10% absolute decline in %FVC, or respiratoryrelated hospitalizations
- All-cause mortality or respiratory-related hospitalizations

Results will be based on the results coming from adjudication. Time to first event will be presented for each type of adjudicated event, similarly as time to first respiratory-related hospitalizations, using Kaplan-Meier tables, graphs and Cox PH models based.

In addition, for all-cause hospitalization and all-cause mortality a frequency table will be provided for the primary cause of death/hospitalization as defined by the CEAC.

Respiratory related events analyses will also be provided by stratification factor (standard of care).

In addition to the analysis of all-cause mortality based on adjudication, a time to all-cause mortality analysis will also be performed on all-cause mortality as reported by the investigator.

Analyses to assess the impact of COVID-19 cases (infection and suspected) on mortality and disease progression will be provided.

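### Kaplan-Meier tables for respiratory-related and all-cause hospitalization, hospitalization for non-elective lung transplant, acute exacerbation and respiratory-related mortality censor competing deaths, so one minus Kaplan-Meier overstates the probability of the event

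*SAP*

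**What the plan says.** SAP 9.3.3 handles the second key secondary endpoint, time to first respiratory-related hospitalization. It plans the number and percentage of subjects with an event, the event rate per 100 patient-years, a Cox model, and Kaplan-Meier estimates: "time to first event will be graphically displayed and tabulated" at each scheduled week and at the last available time point.

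SAP 9.3.3.1 carries the method over to the other adjudicated endpoints, "using Kaplan-Meier tables, graphs and Cox PH models based" (the sentence ends there). The list includes "Mortality: all-cause and respiratory-related", all-cause hospitalization, hospitalization for non-elective lung transplant, and "Acute IPF exacerbation". It also includes several composites that contain all-cause death.

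The censoring paragraph of 9.3.3 has one rule: "If the subject did not have an event, the time to event will be censored at the last contact date". SAP 6.5 then defines last contact. For endpoints that do not use vital status: "The last contact, not including mortality information is defined as the latest date collected in the eCRF from the date of death", followed by the other candidate dates. A death without the event is therefore a censoring. For respiratory-related mortality, a non-respiratory death is not an event, so the same rule censors that subject too.

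SAP 9.1, which lists what version 2.0 drops, removes only the on-treatment and negative binomial analyses from 9.3.3 and does not list 9.3.3.1. These tables remain planned. Neither document names a competing-risk estimator for these endpoints. The cumulative incidence displays in SAP 9.3.2.4 and 9.3.5 are distributions of change in percent predicted FVC and in SGRQ score, which is a different thing.

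**The concern.** A subject who has died cannot later be hospitalized, have an exacerbation or reach transplant. Kaplan-Meier with deaths censored treats that subject as if the event could still occur at the same rate as in the survivors. Its complement estimates what would be seen if nobody died first, and that exceeds the proportion who actually have the event.

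Protocol Section 2 describes IPF as lethal, with "median survival of 2-5 years following diagnosis", and follow-up was planned to reach about 132 weeks for the first subjects enrolled. The excess accumulates with time, so it is largest at the late time points in these tables. If mortality differs between arms, the excess differs too. At stake is how the tabulated event probabilities are read, arm by arm, in a report meant to explain the results and inform future compounds.

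**Working it through.** **Nothing to reproduce.** Neither document states an event rate, event count or event probability for these endpoints. The hazards below are assumptions, shown as a range.

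**Inputs from the documents.** Follow-up of 52 to 132 weeks (Protocol 4.1) and 250 subjects per arm (Protocol 7.1). Median survival of 2 to 5 years from diagnosis (Protocol Section 2) converts, as a constant hazard, to ln 2 / 2 = 0.347 and ln 2 / 5 = 0.139 per year. These are upper-end guides only, for reasons given under the objection.

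**Formulas.** Let L be the yearly event hazard and M the yearly hazard of death without a prior event, both constant.
- Reported with deaths censored: 1-KM = 1 - exp(-L t)
- Actual probability of the event (cumulative incidence): CIF = L/(L+M) × [1 - exp(-(L+M) t)]

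Week 52 is t = 364/365.25 = 0.997 years; week 132 is t = 924/365.25 = 2.530 years.

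**Worked case, L = 0.15, M = 0.05, week 132.** 1-KM = 1 - exp(-0.379) = 31.6%. CIF = 0.75 × [1 - exp(-0.506)] = 29.8%. The excess is 1.8 points.

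**Results for L = 0.15:**

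| M per year | Week 52: 1-KM / CIF / excess | Week 132: 1-KM / CIF / excess |
|---|---|---|
| 0.05 | 13.9% / 13.6% / 0.3 | 31.6% / 29.8% / 1.8 |
| 0.10 | 13.9% / 13.2% / 0.7 | 31.6% / 28.1% / 3.5 |
| 0.139 | 13.9% / 13.0% / 0.9 | 31.6% / 26.9% / 4.7 |
| 0.347 | 13.9% / 11.8% / 2.1 | 31.6% / 21.6% / 10.0 |

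Two arms with the same event hazard and death hazards of 0.05 and 0.10 show the same Kaplan-Meier value at week 132 (31.6%), although 29.8% and 28.1% have the event.

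**Wider range.** For L from 0.05 to 0.25 and M from 0.025 to 0.139, the excess is 0.06 to 1.4 points at week 52 and 0.4 to 6.6 points at week 132.

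**Respiratory-related mortality.** Here M is the non-respiratory death hazard. With a total death hazard of 0.05 to 0.139 and 50% to 85% of deaths respiratory, the excess at week 132 is 0.1 to 1.3 points.

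**Simulation check.** With 250 subjects per arm, 80 weeks of accrual, 52 to 132 weeks of follow-up and 2,000 runs, L = 0.15 at week 100 gave Kaplan-Meier 25.0% against Aalen-Johansen 23.9% for M = 0.05, and 25.0% against 22.9% for M = 0.10. This agrees with the formulas.

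**The case against.** The strongest reply is that Kaplan-Meier with deaths censored is the natural descriptive companion of a cause-specific Cox model, and is too high only if read as the proportion with the event. SAP 9.3.3 reports that proportion separately, with a rate per 100 patient-years. All-cause mortality and the composite of death or respiratory hospitalization are planned as well. All of this stands, and it limits the damage. It does not remove the problem: neither the crude percentage nor the rate gives a probability by week, and a reader will take that from a time-point table.

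The size is also uncertain. The survival figure in Protocol Section 2 runs from diagnosis in IPF generally. Entry required "Estimated minimum life expectancy of at least 30 months for non-IPF related disease", which may lower non-respiratory mortality. M counts only deaths without a prior event, so it lies below total mortality. The halt may have cut follow-up short of 132 weeks. Each of these shrinks the excess without changing its direction.

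Sampling error is of similar or greater size. The binomial standard error with 250 subjects, sqrt[p(1-p)/250], is 2.2 points at 13.6%, against an excess of 0.3. It is 2.9 points at 29.8%, against 1.8, and 2.8 points at 28.1%, against 3.5. This ignores censoring and so is a lower bound, especially at week 132, when few subjects remain under observation.

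Three stronger readings are tempting and not supported:
- A reader might infer that the excess is always greatest in the arm with more deaths. On the absolute scale that fails when event hazards differ: at week 132, L = 0.15 with M = 0.08 gives 31.6% - 28.8% = 2.8 points, while L = 0.10 with M = 0.10 gives 22.4% - 19.9% = 2.5 points. The relative excess is 9.8% and 12.6%.
- A reader might infer that the absolute risks available for weighing benefit and risk are wrong as a whole. The crude percentages and rates are sound, and no text says that the Kaplan-Meier values will serve that purpose.
- A reader might infer that the key secondary test is compromised. Its p-value comes from the Cox model, which remains valid for the cause-specific hazard ratio.

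**Conclusion.** The point holds as a matter of description. For the five endpoints, one minus Kaplan-Meier overstates the probability of having the event by a given week whenever subjects die first, and at a similar event hazard it does so more in the arm with more deaths. The direction follows from the censoring rule; the size rests on assumed constant hazards. In the central case it is negligible to small at one year and a few points by week 132, and less if follow-up was shortened. It reaches about 10 points only if the death hazard without a prior event equals that of a two-year median survival, which is unlikely in this population. Improving the tables is worthwhile, but the trial's conclusions do not depend on it.

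**What to change.** In SAP 9.3.3 and 9.3.3.1, for respiratory-related hospitalization, all-cause hospitalization, hospitalization for non-elective lung transplant and acute IPF exacerbation, present Aalen-Johansen cumulative incidence in the tables and curves, with death without the event as the competing event. For respiratory-related mortality, make non-respiratory death the competing event. Use these in place of one minus Kaplan-Meier, or beside it if comparability with earlier publications is wanted. Label the Cox hazard ratios for these endpoints cause-specific. Keep Kaplan-Meier for all-cause mortality and for the composites that contain all-cause death.

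The cost is slight extra programming, since each endpoint needs its competing event defined, and less direct comparability with earlier Kaplan-Meier publications. The cumulative incidence curves should be read next to mortality, because an arm with more deaths can show fewer events for that reason alone. No new data are needed, and the testing hierarchy is unchanged.

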7.1. Determination of Sample Size

To account for multiple testing due to multiple doses, a Bonferroni approach [9] will be applied to the alpha level with higher priority given to the high-dose group. The primary endpoint will be tested at a 4% level when comparing GLPG1690 600 mg to placebo and a 1% level for GLPG1690 200 mg group versus placebo.

Denoting Δ_{600} and Δ_{200} , the true treatment differences of the two GLPG1690 treatment groups with placebo, and assuming a common standard deviation (SD) on the 52 weeks decline in FVC of 275 mL, the probabilities that 0, 1, or 2 treatment comparisons with placebo are statistically significant, are presented in Table 2. The family-wise error rate is protected at 5% using the Bonferroni procedure. The so-called disjuncture power of the study is the probability that 1 or 2 hypotheses are rejected and is displayed in the right-most column of Table 2.

A meta-analysis of the seven placebo-controlled studies that have been conducted on nintedanib, pirfenidone, and pamrevlumab has revealed that the treatment effect at 52 weeks is estimated to be approximately 119 mL in a treatment-naïve population, the effect observed with nintedanib alone is similar (112 mL) [32]. Little information is available on the expected treatment effect of GLPG1690 in addition to pirfenidone or nintedanib. Table 2 gives an overview of the power for different scenarios for the overall treatment effect in the population of subjects on standard of care (either pirfenidone or nintedanib, or neither pirfenidone nor nintedanib).

Since the linear-slope model on the annual rate of decline in FVC accounts for missing data, the number of subjects randomized and the number of subjects included in the model is expected to be equal. An equal number of 250 subjects will be randomized to each treatment group to have at least 80% power to show a significant effect assuming the 600-mg group has a treatment effect of at least 80 mL in the overall population of treatment naïve and patients on standard of care.

Table 2: Probability of Statistical Significance of 0, 1, or 2 Treatment Comparisons With Placebo

mL	0 Successful	1 Successful	2 Successful	Power
$\Delta_{600}=80$ $\Delta_{200}=80$	6.8%	23.4%	69.9%	93.2%
$\Delta_{600}=80$ $\Delta_{200}=60$	10.1%	46.9%	43.0%	89.9%
$\Delta_{600}=80$ $\Delta_{200}=20$	11.5%	84.4%	4.1%	88.5%
$\Delta_{600}=80$ $\Delta_{200}=0$	11.2%	88.0%	0.7%	88.8%
$\Delta_{600}=90$ $\Delta_{200}=60$	5.1%	51.1%	43.8%	94.9%

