- The rate of decline in FVC will be analyzed using a random coefficient regression model (linear slope model) including sex, age, height, and stratification factor as covariates and a random intercept and slope. The treatment effect is determined by using estimated average slopes for each treatment group on the basis of the treatment*time interaction term from the above mixed model, with time as a continuous factor and treatment as a categorical factor. All available FVC values from baseline to Week 52 will primarily be used, including those from the ETD visit for subjects who discontinued early and do not complete their study visits up to Week 52.
- As a secondary analysis, the same model will be fit using all data until the end of the study.
- The proportion of subjects who have an absolute decline $\geq 10\%$ in %FVC at least once during the study or who die will be analyzed using logistic regression including sex, age, height, and stratum as factors using data up to Week 52.
- In addition, the same will be presented using all data up to the end of the study. A time-to-event analysis may also be used to analyze the composite endpoint of %FVC decline and mortality up to the end of the study.
- The %FVC change from baseline will be analyzed using a similar random coefficient regression model (linear slope model) as FVC in mL.

- Other spirometry endpoints will be summarized descriptively, similar to FVC.

Sensitivity analyses including multiple imputation methods and a per-protocol analysis will be performed to assess the impact of missing data, noncompliance, and protocol violations on the primary efficacy analyses. Additional exploratory analyses and graphical presentations may be performed when deemed useful to better understand the data. Details will be described in the SAP.

Time-to-event Data (Including Hospitalization, First Acute IPF Exacerbation, Mortality, and [Qualifying for] Lung Transplant), Using All Data up to the End of the Study

- Time-to-event endpoints will be graphically presented by Kaplan-Meier estimates. In addition, a Cox proportional-hazards model with terms for age, sex, height, and stratum will be used to analyze the hazard ratios for each dose compared to placebo.

Other Efficacy Endpoints

- A mixed-effects model with treatment, time (as a categorical factor), treatment*time, and baseline total score as factors in the model will be applied to the change from baseline in SGRQ total score.

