# 9.3.1. Level of Significance

Given no market authoristation applicaton for ziritaxestat for the treatment of IPF will be submitted anymore, no pooled analyses combining data from both studies will be performed and the below multiplicity adjustment strategy for countries outside US, does not apply. Only abbreviated CSRs per study will be written as explained earlier in this document.

Statistical tests will be done at a 2-sided level. For the analysis of the primary endpoint, to account for the multiple testing due to two doses being compared to placebo, a Bonferroni approach (Hochberg, 1988) will be used with higher priority given to the high-dose group. The primary endpoint will be tested at a 4% level when comparing GLPG1690 600 mg to placebo and a 1% level for GLPG1690 200 mg group versus placebo.

With respect to the multiplicity adjustment for the key secondary endpoints an additional approach was requested by the compared to European Union (EU) countries. For countries outside US and EU, the EU approach will be applied.

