#### For

The requested a multiplicity adjustment for the key secondary endpoints within each study. A closed-testing hierarchical approach will therefore be used for each dose group separately. The

key secondary endpoints will be ordered as listed in Section 2.2.2.1 and they will be tested at a 4% level when comparing GLPG1690 600 mg to placebo and a 1% level for GLPG1690 200 mg group versus placebo. In this approach, the first key secondary endpoint in a dose group will only be tested if the primary endpoint for that dose group showed significance. The next one will only be tested if the previous one showed significance. These analyses will be presented in the study CSR. Figure 2 details the testing order within each of the identically designed studies.

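### Two of the three key secondary analyses, and the other Cox models, adjust for no baseline lung function: the tests are valid, but some efficiency is given up and chance imbalance in severity goes uncorrected

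*SAP*

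**What the plan says.** Disease progression by Week 52 is the first key secondary endpoint. Protocol 7.3.4 specifies "logistic regression including sex, age, height, and stratum as factors using data up to Week 52". SAP 9.3.2.3 says it will be "analyzed using logistic regression with similar factors in the model as for FVC rate of decline", which leads to the list in SAP 9.3.2.1: sex, age, height and stratification factor.

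Time to first respiratory-related hospitalization is the second. SAP 9.3.3: "A Cox proportional hazards model with terms for age, sex, height, and stratum will be used". SAP 9.3.3.1 and 9.3.4 use the same kind of model for mortality, other hospitalization, exacerbation and transplant-related events.

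The third, change in SGRQ total score, is modelled with its baseline score as a covariate (SAP 9.3.5). The repeated-measures sensitivity analysis of FVC also includes the baseline value (SAP 9.3.2.2.1 and Appendix 3).

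Baseline %FVC and hemoglobin-corrected DLCO are both collected and tabulated (SAP 9.2.1). Baseline spirometry is the average of the usable pre-dose values (SAP 6.4). Randomization is stratified only by background standard of care (Protocol 4.6.1).

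**The concern.** The covariate list suits the model it was written for. In the FVC slope model the baseline measurement belongs to the outcome series and each subject has a random intercept, so sex, age and height serve to explain FVC level. Carried over to a yes/no or time-to-event outcome, the same list says nothing about how severe a subject's lung disease was at entry.

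Nothing else in the design fills that gap. Eligibility sets only floors for lung function (FVC at least 45% and DLCO at least 30% of predicted, Protocol 4.5.1), and stratification does not involve severity. If baseline lung function predicts these events, omitting it from a logistic or Cox model moves the estimated ratio toward 1, costs some power, and leaves any chance difference in severity between arms in the estimate. This touches two key secondary endpoints and the mortality and hospitalization comparisons, where a severity imbalance would be a rival explanation for a difference in either direction.

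**Working it through.** **1. Inputs from the documents.** Protocol 7.1: "An equal number of 250 subjects will be randomized to each treatment group". SAP 9.3.1: "Statistical tests will be done at a 2-sided level". Under the within-study hierarchy the key secondary endpoints are tested at a "4% level when comparing GLPG1690 600 mg to placebo and a 1% level for GLPG1690 200 mg group versus placebo". Protocol 7.1 also gives a standard deviation for the "52 weeks decline in FVC of 275 mL" and assumes the "600-mg group has a treatment effect of at least 80 mL". Those last two concern the primary endpoint only.

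**2. The plan's own power figures.** SE = 275 × √(2/250) = 24.6 mL. For 600 mg at 80 mL, power = Φ(80/24.6 − 2.054) = Φ(1.20) = 88.5%. With correlation 0.5 between the two comparisons (shared placebo arm), the probability of at least one success in the eight rows of Protocol Table 2 comes out at 93.4, 90.0, 88.5, 88.8, 95.1, 56.9, 49.6 and 4.8%. The stated values are 93.2, 89.9, 88.5, 88.8, 94.9, 56.1, 49.4 and 4.8%. They agree within 0.8 points, and the present point does not affect them. Neither document gives power, event rates or effect sizes for the key secondary endpoints.

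**3. What a baseline covariate would add.** Assumptions, none from the documents: conditional HR 0.60 with 15% or 30% placebo events and follow-up uniform from 1.0 to 2.5 years (Cox, 1,500 runs per cell); conditional OR 0.55 with 25% or 35% placebo events (logistic, 4,000 runs per cell). One standardized baseline index stands for lung function and is taken as independent of sex, age, height and stratum, which are left out of both models. There are 250 subjects per arm and a two-sided 4% Wald test. Entries are power without → with the index, in %.

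| Ratio per SD | Cox, 15% events | Cox, 30% events | Logistic, 25% events | Logistic, 35% events |
|---|---|---|---|---|
| 1.0 | 44.1 → 44.5 | 79.2 → 79.2 | 72.2 → 72.3 | 83.3 → 83.4 |
| 1.25 | 43.4 → 44.3 | 75.0 → 75.3 | 71.3 → 71.8 | 81.8 → 82.1 |
| 1.5 | 45.7 → 46.2 | 74.2 → 77.0 | 71.0 → 72.3 | 81.7 → 82.8 |
| 2.0 | 44.7 → 47.4 | 71.4 → 77.3 | 65.9 → 69.8 | 75.8 → 79.6 |
| 2.5 | 41.2 → 45.6 | 66.7 → 79.6 | 61.3 → 67.4 | 71.4 → 77.2 |

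The gains by row are 0 to 0.4 points, 0.3 to 0.9, 0.5 to 2.8, 2.7 to 5.9, and 4.4 to 12.9. Monte Carlo error is about 1.3 points (Cox) and 0.7 points (logistic) per power value, and less for the paired differences.

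**4. Movement of the estimate.** At 2.5 per SD the unadjusted OR averages 0.59 to 0.60 against a conditional 0.55, and the unadjusted HR 0.62 to 0.64 against 0.60.

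**5. Chance imbalance.** With 250 per arm, the between-arm difference in mean of a standardized covariate has SE √(2/250) = 0.089 SD. At a ratio of 2.0 per SD, an imbalance of one SE shifts the log ratio by about 0.089 × ln 2 = 0.062, a factor of e^0.062 = 1.06 on the HR or OR.

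**The case against.** The strongest reply is that this is a choice, not an error. The covariates are prespecified, and a randomized comparison without baseline lung function keeps its significance level. That stands. A reader might infer that the planned tests are biased or invalid, and the documents do not support it. Much of the movement toward 1 is non-collapsibility: the adjusted ratio answers a conditional question, and the less-adjusted ratio is not a wrong answer to its own.

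Second, the size is unknown. A reader might take the upper end of the table as power actually lost. Protocol 4.2 and 4.4 link FVC to mortality trends but give no prognostic strength for the baseline value. For disease progression, baseline %FVC already sets the threshold each subject must cross, and its associations with death and with a measured decline could differ in sign and partly cancel. This stands as a limit on the size, not as a reason to leave the covariate out.

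Third, it would overstate the reach to say that the key secondary tests in general lack baseline adjustment, since SGRQ has it. Reach is limited further because a key secondary endpoint is tested for a dose only after a significant primary result for that dose (SAP 9.3.1), and the studies were halted.

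Fourth, DLCO is the weaker candidate. It is measured by local practice (Protocol 6.5.1.2), and centers may use different prediction formulas (Protocol Appendix 2). Extra terms may also strain models for rare events. Both points stand and shape the fix. %FVC comes from centrally read spirometry and does not share the DLCO problem.

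Last, part of the study team was unblinded after termination (SAP 2.7). Changing the covariates of the confirmatory models now would be post hoc. This also stands.

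**Conclusion.** The omission is plain in both documents and sits oddly beside the baseline adjustment of SGRQ and of the repeated-measures FVC model. The planned tests are valid. The weakness is forgone efficiency and uncorrected chance imbalance in severity, in two of three key secondary analyses and the other Cox models.

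The direction is secure if baseline lung function is prognostic. The size is an assumed range: negligible for a weak covariate, a few points of power for a moderate one, and more than 10 points only in the strongest case examined (2.5 per SD with 30% placebo events in the Cox model). It rests on the assumed event rates and effects above, on a single index in place of %FVC and DLCO, and on the 600 mg comparison at 4%. The 200 mg comparison at 1% was not simulated, nor was the pooled two-study analysis, which will not be performed. With essentially no loss when the covariate is not prognostic, the change was worth making before unblinding. Nothing here shows that the omission explains the trial's outcome.

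**What to change.** In a plan that is still blinded, add baseline %FVC (as defined in SAP 6.4) as a continuous covariate to the disease-progression logistic model and to the Cox models of SAP 9.3.3, 9.3.3.1 and 9.3.4. Keep sex, age, height and stratum. Where event counts allow, add baseline hemoglobin-corrected percent-predicted DLCO as a second covariate, noting that it follows local practice. State that the resulting OR or HR is conditional on these covariates.

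For these studies, leave the prespecified models in place. Report the adjusted models beside them in the abbreviated CSR as labelled supportive analyses, with the reason documented there as the end of SAP 9.1 provides for changes after unblinding.

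Cost: no new data, since both variables are already collected and tabulated. Before unblinding, it takes a few lines of SAP text recording the departure from the covariate list in Protocol 7.3.4, which Protocol section 7 allows the SAP to document. Now, it takes a few additional model runs and table rows.
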